- assess level of satisfaction with the RFWP educational outreach workshops, consultation to department leaders (and referral of their trainees and/or faculty), and clinical services provided to distressed trainees and faculty.

Research Questions:

1. How many trainees and faculty participate in the online, anonymous ISP survey and review the clinician's response to their surveys? In addition, how many highly distressed/high risk (Tier 1) trainees and faculty communicate anonymously with the RFWP clinician (via the dialogue function) and accept referrals or come in for an in-person evaluation?
2. How representative are the ISP participants of the overall OHSU population of SOM trainees and faculty, Providence and Legacy residents that could have participated?
 - a. Hypothesis: we hypothesize a greater overall participation rate from OHSU, Providence, and Legacy trainees and OHSU faculty than seen with UCSD SOM (13%) due to our greater utilization rate at the RFWP, and visibility as an on-site program and the higher response rate to our 2011 anonymous survey (71% among residents/fellows). We are uncertain how many Tier 1 respondents will communicate with our clinicians and agree to services—this question is exploratory.
 - b. Exploratory question re: representativeness—we hope that our participants will be similar to the overall Providence, Legacy and OHSU population so that results will be more generalizable.
3. What is the relationship among level of distress (ISP tiers), type of symptoms reported on ISP and willingness to seek treatment? Is participation in the ISP (as reported in 1st session intake questionnaire) related to response to treatment (change in distress and burnout ratings and risk level, attendance of sessions)?
 - a. Hypothesis: level of distress/risk on the ISP will be positively related to greater willingness to accept referrals or make appointment . We are uncertain if participation in the ISP per self-report on intake paper work will led to different treatment response than others seen at our program. We are uncertain whether respondents with certain symptoms (e.g., substance abuse, suicide risk) may be anxious about communicating with us and to come in for an in-person meeting—this question is exploratory.

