When the ISP has been completed by an individual, the ISP computer immediately analyzes the responses on the questionnaire and classifies the questionnaire into 3 Tiers according to level of distress on the PHQ-9 (a standard depression screen) and level of suicide risk with Tier 1 (highest risk) and 3 (lowest risk). Clinicians are able to review answers to each question and the open-ended question re: recent stressors. The ISP protocol requires clinicians to respond to Tier 1 respondents within 24 hours, Tier 2 in 36 hours and Tier 3 in 48 hours. The clinician sends a response specific to the respondent's tier, introduces himself/herself (provides email, pager) and offers responses. For Tier 1 and 2 respondents, the clinician will urge them to schedule an in-person meeting via official OHSU email or the clinician's pager. For Tier 3 respondents, the clinician may offer an in-person meeting and/or educational/preventive resources (e.g., websites/handouts via the message posted). All respondents will be given the option to dialogue further with the clinician about any concerns/questions they might have via posting responses on the ISP website to the clinician and respondent. Once the clinician posts a response, the computer accesses the respondent's encrypted email address and send a notification that a response is available for viewing. Several reminders will be sent automatically to Tier 1 and 2 students and then 15 and 30 days after the clinician's response is posted. If they did not contact the clinician, a final brief update questionnaire is sent to the respondent to ask about how he/she is doing in the past few weeks and ask about possible reasons for not responding the clinician's invitation to dialogue or meet. Respondents can dialogue with the RFWP clinician as frequently as they need to although the goal is to address their concerns and facilitate them coming in for an in-person evaluation at the RFWP.

An ISP database will be created with this de-identified data for each participant that completes the ISP and will include the responses on their ISP, Tier status, any communications between the participant

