and the RFWP clinician and whether he/she accepted a referral for services and expressed willingness to schedule an in-person evaluation at the RFWP. Note: no identifying information will be included in the ISP database other than gender, broad categories of year of training or faculty status, broad category of age and type of program (e.g., primary care vs. nonprimary care). If the participant reveals his/her name in any communications with the RFWP clinician, this data will be deleted from the ISP database. Appointments will be scheduled outside of the ISP system by instructing the participant to contact the RFWP clinician directly via OHSU email and at that time revealing who they are.

At the first in-person or telehealth (during modified operations under COVID-19, all RFWP visits became telehealth) appointment at the RFWP, the client will be asked to review and sign a (1.) consent form to participate in treatment at the RFWP and (2.) a research consent form. Clients may be given a copy of the research consent form to review and then be given the option to sign the research consent form in subsequent sessions. The research consent form will include wording that the client is giving permission for retrospective data (prior to signature on research consent form) to be included in the study. Due to all visits now being telehealth, the intake paperwork and research consent forms are presented and reviewed in the telehealth session and client then can complete them and email them back to the clinician via secure OHSU email.

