ISP Sample of Residents, Fellows, and Faculty: All OHSU residents and fellows (approximately 800 annually) and all full-time (0.5 FTE) faculty (approximately 3000) will be sent via OHSU email a link to the ISP survey following the RFWP clinician's presentation of the Stress and Depression workshop to their department. Note: only residents, fellows and full-time SOM faculty will be included as they are the only ones who are eligible for services through the RFWP (we don't have capacity to provide services to all adjunct faculty). All Legacy residents (approximately 90 a year) will be invited by RFWP clinicians (during workshops/orientation to these groups) to participate in completing the ISP. Note: new Legacy residents/fellows effective 7/1/21 will no longer be enrolled. All Providence residents (approximately 90 a year) will be invited by RFWP clinicians (during workshops/orientation to these groups) to participate in completing the ISP. *RFWP Client Outcomes Sample:* All patients seen at the RFWP (to start with IRB approval) will be invited to participate in the research study—estimated to be 200-300 annually that are seen at the program. This estimate is based on 17% of 800 OHSU residents/fellows and approximately 2% of 3000 SOM faculty utilizing services through the RFWP in 2012-13. Increased outreach efforts through this proposed project “Reaching Out” will likely raise the visibility of the RFWP (especially among faculty) and lead to a slightly higher number of faculty and medical trainees utilizing future RFWP annually.

All clinical data are entered into an encrypted ACCESS clinical records database that only RFWP clinicians have permission to access. Participants who also complete the Research Study Consent Form will have the following clinical data exported into a research database for analyses: RFWP Subject ID number* randomly assigned (by computer) to the resident, fellow, or faculty member at time of intake,

- demographic and work/training program information (gender, year of birth, ethnic/race, year of training if relevant, resident/faculty status, type of program/specialty) from the “Personal History and Data Form” completed by the patient in the first meeting
- reason for referral, referral source, knowledge of RFWP
- psychological, suicide, and medication history (if relevant) based on clinical interview
- participation in the ISP and ratings of helpfulness of the ISP components (in “Personal Health History and Data Form”)

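### Research question 1 asks how many Tier 1 respondents come in, but tier and attendance sit in separate, unlinked databases, so that part cannot be counted by tier as planned

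*Protocol*

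**What the plan says.** Protocol, Research Questions, item 1, asks how many Tier 1 trainees and faculty communicate anonymously with the clinician through the dialogue function and "accept referrals or come in for an in-person evaluation". Item 2a says the numbers communicating and agreeing to services are uncertain and labels the question exploratory.

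Procedures, ISP Protocol, describes the ISP database. For each completer it "will include the responses on their ISP, Tier status, any communications between the participant" and clinician, and "whether he/she accepted a referral for services and expressed willingness to schedule an in-person evaluation at the RFWP". On anonymity it states that "no identifying information will be included in the ISP database other than gender" and a few other broad categories, and any name a respondent reveals is deleted. On booking: "Appointments will be scheduled outside of the ISP system by instructing the participant to contact the RFWP clinician directly via OHSU email". Tier 1 and 2 respondents are urged to arrange a meeting by OHSU email or the clinician's pager. After the automatic reminders, "If they did not contact the clinician, a final brief update questionnaire is sent to the respondent", asking how they are and why they did not respond.

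Data Collection, Sample and Measures, lists what goes from the clinical records to the research database for clients who sign the research consent. The list includes number and year of sessions, referral source, and "participation in the ISP and ratings of helpfulness of the ISP components". It includes neither tier nor an ISP username. The intake questions described under RFWP Client Outcomes Protocol are likewise limited to whether the ISP was completed and whether it helped.

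**The concern.** The question joins two facts about one person: the tier assigned by the ISP and whether that person later attended. The protocol collects each fact in a different place and keeps the two places apart. A statistical analysis plan could not repair this, because the joining variable is never collected.

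Purpose/Aims says effectiveness will be judged through proxies for suicide risk, among them delivery of mental health services where needed. For the highest-risk group, attendance is the direct measure of that delivery. If stated willingness is reported in its place, the figure includes people who said they would come and did not. The exploratory remark under question 3, on whether respondents with certain symptoms hesitate to come in, meets the same limit if it is read as attendance.

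**Working it through.** The protocol states no count, rate or sample size for this question, so there is no figure to reproduce. The check is to take each element of question 1 and ask which database holds it together with tier.

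| Element for Tier 1 | Held in | Tier in the same record? | Countable by tier? |
|---|---|---|---|
| Used the anonymous dialogue | ISP database | Yes | Yes |
| Accepted a referral or expressed willingness | ISP database | Yes | Yes, where it is recorded there |
| Attended in person | RFWP export (sessions), consenting clients only | No | No |

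The RFWP export can give one related number: self-reported ISP completers who attended, all tiers pooled, among consenting clients.

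**Could the databases be joined?** No key is described. The ISP email address is encrypted and withheld from the clinicians, names are deleted, and identity is revealed only when the person makes contact outside the ISP system. What the two databases share is coarse: gender, training or faculty status, age and type of program.

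**What do the totals say without a link?** Let N be ISP completers, T those in Tier 1, and A completers who attend. The number of Tier 1 attenders lies between max(0, T + A − N) and min(T, A).

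Illustration, using an assumed participation rate, Tier 1 share and attendance:
- Eligible: 800 residents and fellows + 3,000 faculty + 90 Providence residents = 3,890 (Sample and Measures).
- N: 13% of 3,890 = 505.7, taken as 506. This borrows the UCSD participation rate quoted in the protocol as a stand-in.
- T: assumed 10% of 506 = 50.6, taken as 51.
- A: assumed 50.
- Lower bound: 51 + 50 − 506 = −405, so 0.
- Upper bound: min(51, 50) = 50.

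The result does not depend on these particular values. The lower bound is 0 whenever T + A does not exceed N, and the upper bound is simply the smaller of T and A. The observed A would also fall short of the true A, because non-consenting clients are left out.

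**Direct contact.** The route urged on Tier 1 and 2 respondents is email or pager. No step is described that enters such contact in the anonymous ISP record. A respondent who pages without posting could therefore be missing from the uptake fields and be sent the questionnaire meant for those who made no contact. The protocol does not say that this happens, and nothing in it allows the frequency to be estimated.

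**The case against.** The strongest case on the other side has four parts.

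- **The loss is narrow and the question is exploratory.** This stands. Dialogue, referral acceptance and willingness are held with tier. Item 2a speaks of agreeing to services, and the hypothesis under item 3 concerns willingness to accept a referral or make an appointment; both fit the recorded fields. No hypothesis depends on Tier 1 attendance. Exploratory status excuses the lack of a hypothesis, but not a question the data cannot answer.
- **Question 1 may count dialogue users only.** This is a fair reading of the wording. On it, someone who pages without posting is outside the numerator and is not wrongly omitted. The attendance part still needs tier and attendance in one record.
- **Direct contact may in fact be recorded.** This also stands. The ISP database is said to hold any communications with the clinician, with no stated restriction to website posts. The protocol does not define contact for the update questionnaire or show its reply options.
- **Keeping the databases apart is a deliberate safeguard.** It is, since fear about confidentiality is one of the barriers the study addresses. The remedy must not rebuild a link, which limits how much detail may be asked at intake.

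A reader might also infer that the plan cannot tell whether the highest-risk group was reached at all, or that attendance is its only follow-up signal. The documents support neither. Reach through dialogue and acceptance is countable by tier. The update questionnaire asks how respondents are doing, and clients have repeated distress and burnout measures and clinician-rated suicide risk.

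**Conclusion.** The point holds for one part of one exploratory question: the number of Tier 1 respondents who attend cannot be obtained from the data as described. It should be fixed, but it does not undermine the study. The conclusion rests on the listed contents of the two databases being complete and on there being no undescribed key. If either assumption is wrong, the protocol need only say so.

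The 0 to 50 range illustrates how little the unlinked totals reveal; it is not an estimate. It might be inferred that direct contacts leave no trace and are wrongly classed as non-responders. The protocol makes that possible but does not establish it, so no size or direction of bias should be claimed from it.

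**What to change.** 1. Add one optional item to the intake form, beside the existing ISP question, asking what level of distress or risk the ISP feedback gave. Word it by feedback level: the protocol says respondents learn how they scored, but not that they are told a tier number. Add the item to the list of exported fields.
2. Do not ask when the ISP was completed. A date beside the shared demographic categories would make it easier to match records that are meant to stay unlinked.
3. Report question 1 as separate counts: dialogue by tier; accepted referral or stated willingness by tier (both from the ISP database); and attendance by self-reported feedback level among consenting clients. Describe the last as a minimum count, subject to accurate recall. Do not report willingness as attendance.
4. If the item is not added, restate the last part of question 1 as accepted referral or expressed willingness.
5. If the platform allows it and the option is not already there, add a reply to the update questionnaire for respondents who have already contacted the clinician directly.

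The cost is one intake item, possibly one reply option, and a minor IRB amendment. The limits are that the level is self-reported, only consenting clients are covered, and earlier intakes lack the item. Even a coarse feedback level adds a little detail about a small group, which is why the item should be optional and reported only in aggregate.

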depression, substance abuse, eating disorders, and suicide risk. Responses are scored and ranked according to level of distress and risk with Tier 1 representing “high risk, high distress” and Tier 2 “moderate distress, less risk” and Tier 3 “low or no distress or risk”. RFWP clinicians will monitor responses, provide prompt communication back to the participants with information about how they scored, resources available to them, address any questions/concerns they might have and invite them to set up an appointment at the RFWP (if distressed). A similar size academic medical center to OHSU, UCSD, administered this survey to all medical students, residents, fellows, and faculty (13% completed it) and the majority eventually seen by clinicians indicated that they never would have sought help if they had not received feedback on the ISP and been encouraged to come in for evaluation/treatment (Moutier et al., 2012). Being able to anonymously dialogue with a clinician about their specific situation and questions appeared to persuade some participants to come in for an evaluation or accept a referral. This academic medical center did not have an in-house counseling program for residents and faculty like the OHSU RFWP—UCSD trainees received an initial evaluation from a clinician and then were provided with community referrals. Their participation rate of 13% is similar to rates of participation in the ISP in undergraduate populations (e.g., Haas et al., 2008). We hypothesize that our highly visible and utilized RFWP may lead to a higher ISP participation rate among the residents, fellows, and faculty.

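### Hypothesis 3a relates ISP tier to willingness to accept help, but tier also sets how strongly help is offered, so an all-tier gradient describes uptake under the program and cannot by itself show greater willingness

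*Protocol*

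**What the plan says.** Protocol, Research Questions, item 3 asks: "What is the relationship among level of distress (ISP tiers), type of symptoms reported on ISP and willingness to seek treatment". The parenthesis makes tier the measure of distress. Hypothesis 3a gives the direction: "level of distress/risk on the ISP will be positively related to greater willingness to accept referrals or make appointment".

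Protocol, Procedures (ISP Protocol) says that the computer assigns tier from PHQ-9 distress and suicide risk. Tier then governs the contact:

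- Content: "The clinician sends a response specific to the respondent's tier".
- Tiers 1 and 2: "For Tier 1 and 2 respondents, the clinician will urge them to schedule an in-person meeting".
- Tier 3: "For Tier 3 respondents, the clinician may offer an in-person meeting and/or educational/preventive resources".
- Reminders: "Several reminders will be sent automatically to Tier 1 and 2 students". None are stated for Tier 3.
- Timing: clinicians must "respond to Tier 1 respondents within 24 hours, Tier 2 in 36 hours and Tier 3 in 48 hours".

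Some contact is common to all tiers: everyone may dialogue with the clinician, and the notice that a reply is posted is not limited by tier. The ISP database is to hold questionnaire responses, tier, communications, and whether the respondent accepted a referral and expressed willingness to schedule an evaluation.

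The Statistical Analyses section names descriptive, correlational and some multiple regression analyses. It names no specific test for 3a.

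**The concern.** Tier is both the explanatory variable and the rule that decides who is urged and who is reminded, and acceptance is the response to that contact. A respondent in Tier 3 who was never offered a meeting may be counted as not accepting one.

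The protocol itself treats encouragement as something that moves uptake. Under Purpose/Aims it reports that most of those eventually seen at the comparison center said "they never would have sought help if they had not received feedback on the ISP and been encouraged to come in for evaluation/treatment".

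What is at stake is the conclusion from 3a. Reported without qualification, a rising gradient would be read as more distressed clinicians being more willing to seek help, although some or all of it may come from the stronger offer. No sample size or treatment decision depends on 3a.

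**Working it through.** **Where tier and offer are tied.** Tiers 1 and 2 share the stated urging and reminders. They differ in reply window (24 against 36 hours) and in tier-specific wording. Tier 3 differs from both in urging, reminders and window. The stated policies for Tiers 1 and 2 and for Tier 3 do not overlap, so an all-tier comparison cannot separate distress from offer. The problem lies mainly in Tiers 1 and 2 against Tier 3.

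**Is there a figure to reproduce?** No. The protocol gives no sample size, effect size, acceptance rate or tier mix for this question. What follows is an illustration only.

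**Inputs from the protocol.** Eligible pool: 800 residents and fellows + 3,000 faculty + 90 Providence residents = 3,890 (Legacy left out because its enrollment ended). At the comparison center's 13% participation, 0.13 × 3,890 = 506. Hypothesis 2a expects more than 13%; at an assumed 20%, 0.20 × 3,890 = 778.

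**Assumed inputs.** Tier mixes 10/40/50, 20/40/40 and 10/20/70%. Acceptance p3 in Tier 3, and p3 + d in both Tiers 1 and 2, where d is an outreach effect only. Distress has no effect. The test is a Cochran-Armitage trend with scores 2, 1, 0, chosen here because the protocol names none.

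**Formula.** With tier shares m, scores s, mean score s̄ and overall acceptance p̄, expected z = N Σ m(s − s̄)p / √[p̄(1 − p̄) N Σ m(s − s̄)²].

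**Worked case**, mix 10/40/50, p3 = 5%, N = 506:

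- s̄ = 0.1×2 + 0.4×1 = 0.6, and Σ m(s − s̄)² = 0.8 − 0.36 = 0.44.
- Numerator = 506 × (0.1×1.4 + 0.4×0.4) × d = 506 × 0.30 × d; the p3 terms cancel.
- At d = 5.09 points: numerator 7.73; p̄ = 0.05 + 0.5×0.0509 = 0.0755; denominator √(0.0698 × 506 × 0.44) = 3.94; z = 1.96.
- In people: 253 in Tiers 1 and 2 × 0.0509 = about 13 extra acceptances.

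**Outreach uplift that alone gives expected z = 1.96**

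| N | Tier 3 acceptance | Uplift over the three mixes | Extra acceptances |
|---|---|---|---|
| 506 | 5% | 5.1 to 5.65 points | 8 to 17 |
| 506 | 2 to 10% | 3.6 to 7.1 points | 5 to 22 |
| 778 | 2 to 10% | 2.8 to 5.6 points | 6 to 26 |

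**Chance of a significant positive trend from outreach alone** (N = 506, binomial simulation, z > 1.96): 5% against 7.5%, about 16 to 21%; 5% against 10%, 42 to 50%; 5% against 15%, 89 to 93%. With equal acceptance in all tiers it is about 3%, close to the nominal 2.5%.

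**Effect of the denominator.** Suppose 10% of those offered a meeting accept, in every tier, but only half of Tier 3 is offered one. Acceptance among all respondents is then 10% in Tiers 1 and 2 and 0.5 × 10% = 5% in Tier 3. That is the 5% against 10% case above, with no difference in response to an offer.

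**The case against.** The strongest case on the other side is that nothing is stated wrongly. 3a is worded as an association. Outreach by tier is the program, so acceptance under the program is a natural reading of willingness to accept a referral. The Statistical Analyses section prescribes no three-tier test, item 3 also asks about type of symptoms, and a separate analysis plan could add the caveat. The comparison center's evidence mixes feedback with encouragement among people already seen, so it does not size a tier-specific effect. All rates above are assumed.

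Much of this stands, and it rules out four stronger readings that a reader might infer:

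- *That 3a cannot be tested or its result is invalid.* It can be tested, and the association is a sound description of uptake.
- *That the protocol commits to a flawed trend test.* It names no test for 3a.
- *That outreach would explain the gradient.* The document has no data on this. The figures show only that a modest gap would be enough.
- *That a regression on PHQ-9 and suicide risk within Tiers 1 and 2 would isolate distress.* Clinicians can see each answer and messages are personalized, so encouragement may still follow distress. In an illustration where encouragement alone raised acceptance with PHQ-9 within these tiers, the tier-adjusted joint test of PHQ-9 and risk rejected in about 9% of runs (acceptance rising from 10% to 20%) or 27% (from 5% to 30%), against a nominal 5%. Tier is also built from the same items, so adjusting for it removes signal.

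What the objection does not remove is that item 3 names tier as distress, 3a names willingness as the outcome, and Procedures makes the offer depend on tier. That follows from the protocol's own text, whatever an analysis plan adds.

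**Conclusion.** The point holds as a limit on interpretation. A positive association between tier and acceptance across all three tiers would be a valid result about uptake under tier-specific outreach. It would not by itself support the conclusion that more distressed respondents are more willing.

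The logic rests on the protocol's text alone. The size does not: the outreach share cannot be computed from the document, and the uplift of about 5 to 6 points (8 to 17 acceptances among 152 to 304 people) depends on assumed acceptance, tier mix, participation and test. The change is a cheap improvement to one of nine research questions, and it affects only what 3a can conclude.

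**What to change.** Leave outreach as it is, and make these changes to the reporting of 3a:

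1. State that any all-tier result will be reported as the association of tier together with its tier-specific outreach, and not as distress-driven willingness.
2. From the stored communications, report by tier how many respondents were offered a meeting. Give acceptance among those offered as well as among all respondents. The first figure removes the denominator problem, but it is not a clean comparison: Tier 3 offers are discretionary, so those offered may be selected, and reminders still differ.
3. Optionally, and as exploratory only, relate acceptance to PHQ-9 and suicide-risk responses within Tiers 1 and 2, where both tiers are urged and reminded. State with it that:
   - encouragement may still track distress;
   - the range of distress is restricted, since Tier 3 (40 to 70% of respondents under the assumed mixes) is left out;
   - power is low. In simulation with N = 506, 10% acceptance and equal outreach, tier-adjusted power was 38 to 60% for an odds ratio of 2.0 per 5 PHQ-9 points, and 17 to 34% when the effect ran through a PHQ-9-plus-risk composite (odds ratio 1.5 per unit);
   - a null result is not evidence against 3a.

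The cost is one reporting sentence, one table and, if wanted, one exploratory model. The ISP database already provides for the data, though communications must be coded for whether a meeting was offered. The price is a more limited conclusion for 3a.
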